8.4.5. Physical Examination

The occurrence of a physical examination and the date and time, along with the results of the mental status exam and the abbreviated neurological exam are collected. These will be presented in individual participant data listings only. After screening, any clinically significant abnormal findings in physical examinations will be reported as AEs.

8.6. Other Patient-Reported Assessments

The Patient Perception of Response Burden Questionnaire is a patient-reported measure that assesses the multidimensional construct of response burden. Participants respond to 6 items assessing 1) how well the questions related to their actual concerns, 2) how comfortable the participants were with answering the questions, 3) how well the survey characterized their health and well-being, 4) the length of time to complete the questionnaires, 5) whether questions seemed unimportant or repetitive, and 6) what additional information should have been gathered. Items 1 to 3 are assessed on a 0 to 10 scale, item 4 is assessed on a 1 to 3 scale, and items 5 and 6 are open-ended. Items 1 and 4 are reverse scored. A composite score can be calculated to create a weighted representative index of relevance, comfort, and well-being relative to time to completion (i.e., items 1, 2, and 3 were summed and multiplied by item 4) for a range of 0 to 72, with higher scores indicative of elevated endorsed response burden. The open-ended items will be summarized thematically. The Patient Perception of Response Burden Questionnaire will be performed as specified in the Schedule of Assessments.

This questionnaire will be analyzed as post-hoc.

8.7. Other Analysis

Not applicable.

9. SUMMARY OF INTERIM AND DMC ANALYSES

9.1. Interim Analysis

The sponsor may conduct an interim analysis. Detailed descriptions of planned data analyses will be provided in a separate interim SAP, if applicable.

9.2. DMC Analysis

Not applicable.

APPENDIX A. SCHEDULE OF ASSESSMENTS

Schedule of Assessments

Assessment	Screening	Treatment Period										Follow-up Period	
		-28 to -1	1	5 (± 1) Phone Call	8 (± 1)	12 (± 1) Phone Call	15 (± 1)	19 (± 1) Phone Call	22 (± 1)	26 (± 1) Phone Call	29 (+1) EOT		
Study Day													
Informed Consent	X												
Inclusion/Exclusion	X												
Demographics	X												
Medical History	X												
Pregnancy Test	X (serum; all women)	X (urine ; WOC BP only)					X (urine; WOCBP only)				X (urine; WOCBP only)		X (urine; WOCBP only)
FSH (postmenopausal women only)	X												
Randomization ^a		X											
Alcohol/cotinine screens		X		X			X		X		X		
Drug screen	X	X											
Physical examination ^b	X	X		X			X		X		X		X
Neurological examination including MSE ^b	X	X		X			X		X		X		X

Assessment	Screening	Treatment Period										Follow-up Period	
		1	5 (± 1) Phone Call	8 (± 1)	12 (± 1) Phone Call	15 (± 1)	19 (± 1) Phone Call	22 (± 1)	26 (± 1) Phone Call	29 (+1) EOT	35 (± 1) Safety Phone Call		
Study Day	-28 to -1												
Body height	X												
Body weight	X												
Vital signs ^c	X	X		X		X		X		X			X
12-Lead ECG ^d	X	X		X		X		X		X			X
Chemistry/hematology/ coagulation/urinalysis	X	X		X		X		X		X			X
Kinesia ^f	X	X		X		X		X		X			X
TETRAS ^g	X	X		X		X		X		X			X

Assessment	Screening	Treatment Period										Follow-up Period					
		1	5 (± 1) Phone Call	8 (± 1)	12 (± 1) Phone Call	15 (± 1)	19 (± 1) Phone Call	22 (± 1)	26 (± 1) Phone Call	29 (+1) EOT	35 (± 1) Safety Phone Call						
Study Day	-28 to -1																
Patient Perception of Response Burden											X		X				
Participant training ^h	X	X															
Dispense study drug		X		X		X		X									
IP administration		Administered once daily for 28 days								Not applicable							
AEs/SAEs		X															
Prior and concomitant medication and history ⁱ		X															

Abbreviations: ADL = activities of daily living; AE = adverse event; [REDACTED]

[REDACTED]; ECG = electrocardiogram; EOS = end of study; EOT = end of treatment; [REDACTED]

[REDACTED] ETV = early termination visit;

FSH = follicle stimulating hormone; HIV = human immunodeficiency virus; ICF = informed consent form; min = minutes; IP = investigational product; MSE = mental state examination; [REDACTED]

SAE = serious adverse event; TETRAS = The Essential Tremor Rating Assessment Scale; WOCBP = women of childbearing potential

Note:

- The suggested order of assessments during clinic visits is: vital signs, TETRAS, Kinesia, ECG, blood sample collection for [REDACTED] clinical laboratory assessments, and questionnaires.
- All assessments will be performed predose unless specified in a footnote.

^a Randomization will occur on Day 1 after meeting all eligibility criteria.

^b Complete physical examinations (including MSE and neurologic examination as parts of physical examination) should be performed as specified and as clinically necessary (see Section 12.1.3 of the protocol).

^c Predose on Day, supine and standing blood pressure and heart rate will be collected in triplicate at least 15 minutes apart, measured after the participant has been in the supine position for at least 5 minutes and then repeated 1 minute and 3 minutes after standing. Respiratory rate and temperature are collected once predose on Day 1. Vital signs will be collected once predose at all other visits. All postdose vital signs will be collected once at approximately 3 hours (\pm 60 min) after dosing.

^d ECGs will be collected and read centrally. ECGs will be performed predose and approximately 3 hours (\pm 60 min) postdose. All ECGs must be performed after the participant has been in a supine position for at least 5 minutes.

^g The TETRAS Performance and TETRAS ADL subscales will be assessed at Screening and predose at each clinic visit. The TETRAS Performance subscale part 4 upper limb tremor will be assessed simultaneous to Kinesia ONE. In addition, on Day 15, the TETRAS Performance subscale will be assessed at 5 and 8 hours (\pm 30 min) postdose. A videographer will record each TETRAS administration.

^h Participants will be trained by study personnel on the use of software applications, Investigational Product diary, and devices necessary for the conduct of the study.

ⁱ Prior medications will be recorded during Screening and will include all medications and supplements taken within the 30 days prior to signing the ICF through the first dose of IP, as well as a complete history of all treatments for ET since the year of diagnosis. Concomitant medications will be recorded thereafter throughout the duration of the study.

APPENDIX B. HANDLING OF MISSING DATES

Partial dates will adhere to the following conventions in order to classify TEAEs and to classify prior and concomitant medications.

In general, listings will present the actual partial or missing values rather than the imputed values that may be used in derivation.

Adverse Events

In the event of a missing/incomplete start or stop date associated with an adverse event, only the treatment-emergence will be imputed using the algorithm below. Dates will not be imputed.

In general, if the missing/incomplete start date is not clearly prior to initiation of treatment, then the AE will be considered at TEAE.

If the AE end date is prior to the initiation of treatment, the AE will not be considered a TEAE.

If the AE end date is on or after the initiation of treatment:

- If the AE start date is completely missing or if the year is missing, then the AE will be considered a TEAE
- For partial AE start dates:
 - Known year, unknown month and day (or known year and day, unknown month)
 - If the year is the same as or later than the year of the first dose, the AE will be considered a TEAE
 - Otherwise, the AE will not be considered a TEAE
 - Known year and month, unknown day
 - If the month and year are the same as or later than the month and year of the first dose, the AE will be considered a TEAE
 - Otherwise, the AE will not be considered a TEAE

Prior and Concomitant Medications

No imputation process will be used to estimate missing data, except for the purposes of classifying medications as prior and/or concomitant. The following algorithms will be used for partially missing dates.

For start dates of medication uses:

- The day and month are missing: if the participant started receiving the study dosing in the reported year, the first dosing date will be used as the start date; otherwise '01 January' will be used as the start date.

- The day is missing: if the participant started receiving the study dosing in the reported month and year, the first dosing date will be used as the start date; otherwise, the first day of the reported month and year will be used as the start date.

For stop dates of events or medication uses:

- The day and month are missing: if the study end date is in the reported year, the study end date will be used as the stop date; otherwise, '31 December' will be used as the stop date.
- The day is missing: if the study end date is in the reported month and year, the study end date will be used as the stop date; otherwise, the end of the reported month and year will be used as the stop date.

If a medication has the stop date completely missing or missing the year, this medication will be considered as ongoing and concomitant. If a subject is missing a treatment start date, medication will not be classified as either prior or concomitant.

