9.2.2. Prohibited Medications

Use or consumption of the following is prohibited for the timeframes specified:

- Treatment with an investigational drug or device during the 30 days or 5 half-lives (if known) of the investigational drug, whichever is longer, prior to Day 1 or during the study.
- Use of tremorgenic drugs within the 14 days or 5 half-lives (whichever is longer) of Day 1 or during the study.
- Use of agents known to affect SAGE-324 drug metabolism (any known cytochrome P450 3A4 inhibitors and/or inducers) within the 14 days or 5 half-lives (whichever is longer) of Day 1 and through Day 29 of the study period. Use of mild cytochrome P inhibitors and/or inducers may be permitted.
- Concomitant use of sedative/hypnotic drugs for 14 days or 5 half-lives prior to Day 1 and during the 28-day dosing period.
- Any prior ET medications must be discontinued prior to the Screening TETRAS:
 - There must be 14 days or 5 half-lives (whichever is longer) washout period prior to the Day 1 (baseline) visit.
 - For drugs requiring downtitration, there must be the required number of days for downtitration plus 14 days or 5 half-lives (whichever is longer) prior to the Day 1 (baseline) visit.

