8.2.5. Prior and Concomitant Medications

Medications will be recorded at each study visit and coded into drug class (anatomical therapeutic chemical [ATC] Level 2) and PT using World Health Organization-Drug dictionary (WHO-DD) Global B3 September 2019, or later.

All medications taken within 30 days prior to informed consent through the duration of the study (including start and end dates, route, dose/units, frequency, and indication) will be recorded on the electronic case report form (eCRF); all psychotropic medications taken in the 30 days prior to screening will also be recorded. Those medications taken prior to the initiation of the investigational product will be denoted “Prior”. Those medications taken prior to the initiation of the investigational product and continuing beyond the initiation of the investigational product or those medications started at the same time or after the initiation of the investigational product will be denoted “Concomitant”. Note that medication taken before the initial dosing of investigational product and continued after the initial dosing will be categorized as a prior medication and separately as a concomitant medication.

Medications will be flagged in the listing according to whether they are “Prior” or “Concomitant” as defined above. In the event of a missing start or stop date associated with a medication, only the classification (prior and/or concomitant) will be imputed using the algorithm described in [Appendix B](#). Dates will not be imputed.

Details of prior and concomitant medications will be listed by participant, start date, and verbatim term. Prior and concomitant medications will be summarized separately for the Safety Set as the number and percentage of participants with each medication at both the ATC and PT levels.

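### The SAP's partial-date rule for medications ignores a known stop date, so a drug stopped before Day 1 can be counted as Concomitant in the medication tables

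*SAP*

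**What the plan says.** SAP 8.2.5 says that when a medication's start or stop date is missing, "only the classification (prior and/or concomitant) will be imputed using the algorithm described in" Appendix B. It defines Prior by use before the investigational product began. Concomitant covers use that continues past that point, and also "those medications started at the same time or after the initiation of the investigational product will be denoted" Concomitant. One medication may carry both labels.

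For a start date of which only the year is known, Appendix B says: "if the participant started receiving the study dosing in the reported year, the first dosing date will be used as the start date". A reported year other than the first-dose year has its own fallback: "otherwise '01 January' will be used as the start date". For a start date with month and year known but no day, the rule is: "if the participant started receiving the study dosing in the reported month and year, the first dosing date will be used as the start date". Failing that, the first of the reported month is used. None of these rules refers to the stop date. The only closing rule that uses the stop date to set the class is: "If a medication has the stop date completely missing or missing the year, this medication will be considered as ongoing and concomitant".

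The adverse-event half of the same appendix does test the end date: "If the AE end date is prior to the initiation of treatment, the AE will not be considered a TEAE".

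Protocol Amendment 4, Section 13.6.6, presumes a medication concomitant only where its dates are incomplete and its status is also unclear.

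**The concern.** The start-date rule can overrule a fact that is already recorded. If the stop date is known and falls before the first dose, the drug was not taken with study treatment, however little is known about when it began. The rule still moves the start to the first dosing date, which is later than the stop, and 8.2.5 then makes the drug Concomitant.

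This matters somewhat more in a washout trial than elsewhere, because stops shortly before Day 1 are part of the design. Protocol 9.2.2 states: "Any prior ET medications must be discontinued prior to the Screening TETRAS", with a washout of at least 14 days or 5 half-lives before Day 1. SAP Appendix A (footnote i) also places the history of ET treatments under prior medications. At stake is the accuracy of the two Safety Set summaries, Table 14.1.7.1 (Prior) and Table 14.1.7.2 (Concomitant).

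**Working it through.** The plan gives no figure to reproduce. The check applies the written rules to example records.

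**Inputs**
- Start-date rules: SAP Appendix B.
- Definitions of Prior and Concomitant: SAP 8.2.5.
- First dose 22 Mar 2021 and known stop 5 Mar 2021: assumed for illustration. The gap is 22 − 5 = 17 days, which meets the 14-day part of the washout.

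**Rule as written**
- Day and month missing: imputed start = first dosing date if the start year equals the first-dose year; otherwise 1 January of the start year.
- Day missing: imputed start = first dosing date if the start month and year equal those of first dose; otherwise the first of that month.
- Concomitant if the start is on or after first dose, or if the start is before first dose and use continues beyond it.

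| Recorded start | Imputed start | After the stop? | Class as written | Class with a stop-date check |
|---|---|---|---|---|
| 2021, month unknown | 22 Mar 2021 | Yes, by 17 days | Concomitant | Prior |
| Mar 2021, day unknown | 22 Mar 2021 | Yes, by 17 days | Concomitant | Prior |
| 2018, month unknown | 1 Jan 2018 | No | Prior | Prior |
| Feb 2021, day unknown | 1 Feb 2021 | No | Prior | Prior |
| 10 Jan 2021, complete | none needed | No | Prior | Prior |

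The first two records fail, and the stop-date check corrects them without altering the other three.

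**Is the failure confined to particular dates?** Every first-dose day of an assumed 365-day year was combined with known stops 14 to 58 days earlier, which is 365 × 45 = 16,425 combinations.
- Stop in the first-dose year, start month unknown in that year: 14,805 combinations, all 14,805 classed Concomitant.
- Stop in the first-dose month, start day unknown in that month: 1,720 combinations, all 1,720 classed Concomitant.

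Once the trigger is met, the error always follows. These counts do not show how often the trigger is met, because only combinations meeting it were counted.

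**Does another rule prevent it?** The closing rule in Appendix B concerns a stop date that is wholly missing or lacks its year. It does not cover a known stop before Day 1.

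**The case against.** The strongest case on the other side is that little depends on this flag.

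- **Primary result.** A reader might infer that it is affected. The documents do not support that. The primary model in SAP 8.3.3.1.1 contains treatment, baseline score, timepoint and timepoint-by-treatment; the flag is not a term.
- **Deviation review.** A reader might infer that false deviations would follow. SAP 8.2.2 has deviations captured on the eCRF and categorized by the study team, not derived from this flag.
- **Real use hidden by artefact.** A reader might infer that genuine use of tremor drugs on treatment could not be told from misclassified records. Appendix B has the listings show the actual partial values, and Listing 16.2.4.3.2 covers concomitant medications, so a stop before Day 1 would be visible there.
- **Frequency.** The long ET history does not make the error common. A start in an earlier year goes to 1 January of that year and is classed Prior, and eligibility requires ET of at least 3 years' duration. The drug must have been started and stopped within the first-dose year, with the start month unknown. The day-unknown branch is narrower still for ET drugs: a 14-day washout inside one month requires a first dose on the 15th or later (15 − 14 = 1).
- **Reading of Prior.** A drug with a known stop before Day 1 meets the definition of Prior on observed data, so one could flag it as both.

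The first four points stand and set the limits of the finding. The fifth rescues the Prior count only; the drug is still counted as Concomitant. Nor can the rule be defended as a conservative default, since such a default settles what is unknown and here the stop date is known.

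**Conclusion.** The medication rule is wrong as written, and the error is narrow. A partial start in the first-dose year (or in the first-dose month, if only the day is missing) combined with a known stop before first dose gives an impossible date order and a Concomitant label. Read literally, the drug also drops out of Prior. This conflicts with Protocol 13.6.6 and with the logic of the adverse-event rule beside it.

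The effect is limited to the Prior/Concomitant flag and to Tables 14.1.7.1 and 14.1.7.2. The number of affected records cannot be estimated from the documents and is probably small. The conclusion assumes that the appendix is programmed literally; a programmer who lets an observed stop before Day 1 settle the class would avoid the error, but the SAP does not say to do so.

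**What to change.** Add a first step to the medication rules in Appendix B: if the stop date, or the latest date that a partial stop date allows, is before the first dose, classify the medication as Prior only. Otherwise apply the existing start-date rule, with the imputed start never later than the stop date.

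The cost is a sentence or two in the SAP and a small programming change. No new data are needed, and no efficacy output changes. It is best made before database lock, since SAP Section 2 requires later changes to be documented and discussed in the clinical study report.

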APPENDIX C. LIST OF DISPLAYS

Tables

14.1.1	Disposition of Participants (All Subjects)
14.1.2	Analysis Sets (All Subjects)
14.1.3.1	Major Protocol Deviations (Safety Set)
14.1.3.2	Protocol Deviations Related to Covid-19 (Safety Set)
14.1.4.1	Demographics and Baseline Characteristics (Safety Set)
14.1.4.2	Demographics and Baseline Characteristics - Subgroups (Safety Set)
14.1.5	Summary of Disease History (Safety Set)
14.1.6	Medical/Surgical History (Safety Set)
14.1.7.1	Prior Medications (Safety Set)
14.1.7.2	Concomitant Medications (Safety Set)
14.1.8.1	Study Drug Exposure (Safety Set)
14.1.8.2	Study Drug Adherence (Safety Set)
14.2.1.1	Summary of Essential Tremor Rating Assessment Scale (TETRAS) Performance Subscale Part 4 Upper Limb Tremor Score (Full Analysis Set)
14.2.1.2	Change from Baseline in the Essential Tremor Rating Assessment Scale (TETRAS) Performance Subscale Part 4 Upper Limb Tremor Score – Mixed Effect Model for Repeated Measures (MMRM) (Full Analysis Set)
14.2.1.3.1	Change from Baseline in the Essential Tremor Rating Assessment Scale (TETRAS) Performance Subscale Part 4 Upper Limb Tremor Score – Sensitivity Analysis – Missing Data Imputation (Full Analysis Set)
14.2.1.3.2	Change from Baseline in the Essential Tremor Rating Scale (TETRAS) Assessment Performance Subscale Part 4 Upper Limb Tremor Score – Sensitivity Analysis – Excluding Subjects From Sites 001, 002, 003, 004, 007, 008, 010, 011, 017, 019, 021, 023, 024 (Full Analysis Set)
14.2.1.4	Summary of Essential Tremor Rating Assessment Scale (TETRAS) Performance Subscale Part 4 Upper Limb Tremor Score (Per Protocol Set)
14.2.1.5	Change from Baseline in the Essential Tremor Rating Assessment Scale (TETRAS) Performance Subscale Part 4 Upper Limb Tremor Score – Mixed Effect Model for Repeated Measures (MMRM) (Per Protocol Set)
14.2.1.6	Summary of Essential Tremor Rating Assessment Scale (TETRAS) Performance Subscale Part 4 Upper Limb Tremor Score by Subgroup, Total Score (Full Analysis Set)
14.2.1.7	Change from Baseline in the Essential Tremor Rating Assessment Scale (TETRAS) Performance Subscale Part 4 Upper Limb Tremor Score by Subgroup, Total Score - Mixed Effect Model for Repeated Measures (MMRM) (Full Analysis Set)
14.2.2.1	Summary of Essential Tremor Rating Assessment Scale (TETRAS) ADL (Full Analysis Set)

14.2.2.2	Change from Baseline in the Essential Tremor Rating Assessment Scale (TETRAS) ADL – Mixed Effect Model for Repeated Measures (MMRM) (Full Analysis Set) 37
14.2.2.3	Summary of Essential Tremor Rating Assessment Scale (TETRAS) ADL (Per Protocol Set)
14.2.2.4	Change from Baseline in the Essential Tremor Rating Assessment Scale (TETRAS) ADL – Mixed Effect Model for Repeated Measures (MMRM) (Per Protocol Set)
14.2.2.5	Summary of Essential Tremor Rating Assessment Scale (TETRAS) ADL by Subgroup, Total Score (Full Analysis Set)
14.2.2.6	Change from Baseline in the Essential Tremor Rating Assessment Scale (TETRAS) ADL by Subgroup, Total Score – Mixed Effect Model for Repeated Measures (MMRM) (Full Analysis Set)
14.2.3.1	Summary of Essential Tremor Rating Assessment Scale (TETRAS) Performance Subscale (Full Analysis Set)
14.2.3.2	Change from Baseline in the Essential Tremor Rating Assessment Scale (TETRAS) Performance Subscale – Mixed Effect Model for Repeated Measures (MMRM) (Full Analysis Set)
14.2.3.3	Summary of Essential Tremor Rating Assessment Scale (TETRAS) Performance Subscale (Per Protocol Set)
14.2.3.4	Change from Baseline in the Essential Tremor Rating Assessment Scale (TETRAS) Performance Subscale – Mixed Effect Model for Repeated Measures (MMRM) (Per Protocol Set)
14.2.3.5	Summary of Essential Tremor Rating Assessment Scale (TETRAS) Performance Subscale by Subgroup, Total Score (Full Analysis Set)
14.2.3.6	Change from Baseline in the Essential Tremor Rating Assessment Scale (TETRAS) Performance Subscale by Subgroup, Total Score – Mixed Effect Model for Repeated Measures (MMRM) (Full Analysis Set)
14.2.3.7	Summary of Essential Tremor Rating Assessment Scale (TETRAS) Performance Subscale Part 4/6/7/8 Score (Full Analysis Set)
14.2.3.8	Change from Baseline in Essential Tremor Rating Assessment Scale (TETRAS) Performance Subscale Part 4/6/7/8 Score – Mixed Effect Model for Repeated Measures (MMRM) (Full Analysis Set)
14.2.3.9	Summary of Essential Tremor Rating Assessment Scale (TETRAS) Performance Subscale Part 4/6/7/8 Score (Per Protocol Set)
14.2.3.10	Change from Baseline in Essential Tremor Rating Assessment Scale (TETRAS) Performance Subscale Part 4/6/7/8 Score – Mixed Effect Model for Repeated Measures (MMRM) (Per Protocol Set)
14.2.3.11	Summary of Essential Tremor Rating Assessment Scale (TETRAS) Performance Subscale Part 4/6/7/8 Score by Subgroup (Full Analysis Set)
14.2.3.12	Change from Baseline in Essential Tremor Rating Assessment Scale (TETRAS) Performance Subscale Part 4/6/7/8 Score by Subgroup – Mixed Effect Model for Repeated Measures (MMRM) (Full Analysis Set)
14.2.4.1	Summary of Kinesia ONE™ Accelerometer Score (Full Analysis Set) 59

14.2.4.2	Change from Baseline in Kinesia ONE™ Accelerometer Score – Mixed Effect Model for Repeated Measures (MMRM) (Full Analysis Set)
14.2.4.3	Summary of Kinesia ONE™ Accelerometer Score (Per Protocol Set)
14.2.4.4	Change from Baseline in Kinesia ONE™ Accelerometer Score – Mixed Effect Model for Repeated Measures (MMRM) (Per Protocol Set)

14.3.1.1	Summary of Treatment-Emergent Adverse Events (Safety Set)
14.3.1.2	Treatment-Emergent Adverse Events by System Organ Class and Preferred Term (Safety Set)
14.3.1.3	Treatment-Emergent Adverse Events by Preferred Term (Safety Set)
14.3.1.4	Serious Treatment-Emergent Adverse Events by System Organ Class and Preferred Term (Safety Set)
14.3.1.5	Treatment-Emergent Adverse Events Leading to Treatment Discontinuation by System Organ Class and Preferred Term (Safety Set)
14.3.1.6	Treatment-Emergent Adverse Events Leading to Study Discontinuation by System Organ Class and Preferred Term (Safety Set)
14.3.1.7	Treatment-Emergent Adverse Events by Maximum Severity (Safety Set)
14.3.1.8	Treatment-Emergent Adverse Events by Maximum Relationship to Study Treatment (Safety Set)
14.3.1.9	Serious Treatment-Emergent Adverse Events by Preferred Term (Safety Set)
14.3.2.1	Listing of Serious Adverse Events (Safety Set)
14.3.2.2	Listing of Deaths (Safety Set)
14.3.2.3	Listing of Adverse Events Leading to Treatment Reduction/Discontinuation (Safety Set)
14.3.2.4	Listing of Adverse Events Leading to Study Discontinuation (Safety Set)
14.3.4.1.1	Summary of Clinical Chemistry (Safety Set)
14.3.4.2.1	Summary of Hematology (Safety Set)
14.3.4.3.1	Summary of Coagulation (Safety Set)
14.3.4.4.1. 1	Summary of Urinalysis, Continuous Parameters (Safety Set)
14.3.4.4.1. 2	Summary of Urinalysis, Categorical Parameters (Safety Set)
14.3.4.5.1	Summary of 12-Lead Electrocardiogram (Safety Set)

14.3.4.6.1	Summary of Vital Signs (Safety Set)
------------	--------------------------------------------

Listings

[figure not shown]
16.2.1.1	Subject Disposition
16.2.1.2	Screen Failures
16.2.2.1	Inclusion/Exclusion Criteria Violations
16.2.2.2.1	Inappropriate Study Drug Consumption
16.2.2.2.2	Protocol Deviations
16.2.3	Analysis Sets
16.2.4.1	Demographics and Informed Consent
16.2.4.2.1	Medical/Surgical History
16.2.4.2.2	Essential Tremor Disease History
16.2.4.3.1	Prior Medications
16.2.4.3.2	Concomitant Medications
16.2.5.1	Study Drug Dispensation and Return
16.2.5.2	Study Drug Administration
16.2.5.3	Study Drug Exposure and Adherence
16.2.6.1.1	Essential Tremor Rating Assessment Scale (TETRAS) – Performance Subscale Part 4 Upper Limb Tremor
16.2.6.1.2	Essential Tremor Rating Assessment Scale (TETRAS) – Performance Subscales
16.2.6.1.3	Essential Tremor Rating Assessment Scale (TETRAS) – Activities of Daily Living
16.2.6.2	Kinesia ONE™ Accelerometer Score

[figure not shown]
16.2.7.1	Adverse Events	
16.2.8.1.1	Clinical Chemistry	
16.2.8.1.2	Hematology	
16.2.8.1.3	Coagulation	
16.2.8.1.4	Urinalysis	
16.2.8.2.1	Pregnancy Test	
16.2.8.2.2	FSH Testing	
16.2.8.2.3	Local Drug Screen	
16.2.8.2.4	Local Alcohol and Cotinine Screen	
16.2.8.3	12-Lead Electrocardiogram (ECG)	
16.2.8.4	Vital Signs	
16.2.8.5	Physical Examinations	
16.2.8.6	Mental Status Examination	
16.2.8.7	Abbreviated Neurological Examination	
16.2.8.9	Phone Call During Treatment and Follow-up Period	

[figure not shown]
Figures

14.2.1.1.1	Least Squares Mean Change from Baseline in TETRAS Performance Subscale Part 4 Upper Limb Tremor Score by Time Point (Full Analysis Set)
14.2.1.1.2	Forest Plot of Change from Baseline in TETRAS Performance Subscale Part 4 Upper Limb Tremor Score at Day 29, Total Score (Full Analysis Set)
14.2.1.2	Least Squares Mean Change from Baseline in TETRAS Performance Subscale Part 4 Upper Limb Tremor Score by Time Point (Per Protocol Set)
14.2.2.1.1	Least Squares Mean Change from Baseline in TETRAS ADL Score by Time Point (Full Analysis Set)
14.2.2.1.2	Forest Plot of Change from Baseline in TETRAS ADL Score at Day 29, Total Score (Full Analysis Set)
14.2.2.2	Least Squares Mean Change from Baseline in TETRAS ADL Score by Time Point (Per Protocol Set)
